Background and rationale	
The Truenat MTB (including both MTB and MTB plus) and the MTB-RIF Dx reflex assays (Molbio Diagnostics; Bangalore, India) utilize chip-based real-time micro PCR for detection of tuberculosis (TB) and rifampicin (RIF) resistance from DNA extracted from sputum samples in about 25 minutes.
 
A pilot trial conducted in India of the Truenat MTB assay found the assay to achieve high clinical performance. However, further evidence of the Truenat MTB as well as the Truenat MTB-RIF Dx assay, is needed prior to recommending the clinical use of the assays.
 
Prior studies have been conducted as part of a three-phase/stage approach i) a validation of the Truenat MTB assays and MTB-RIF Dx assay diagnostic performance on frozen samples and ii) an operational assessment of the assays performance. The current trial corresponds to iii) the evaluation trial to confirm the diagnostic accuracy and to ensure that the performance characteristics will be consistent in the sites of intended use in a geographical diverse population (microscopy centre level).
 
Further evidence on the diagnostic performance and patient important outcomes on the use of the Truenat MTB assays and MTB-RIF Dx assay at the microscopy centre level is needed to inform potential policy recommendations.

Objectives	
 1. Primary objectives: to determine the diagnostic accuracy of the Truenat MTB assays and MTB-RIF Dx assay using culture and phenotypic/genotypic drug susceptibility test (DST) as gold standard in the intended setting of use. 2. Secondary objectives: to determine the diagnostic accuracy of the Truenat MTB assays and MTB-RIF Dx assay compared to Xpert MTB/RIF using culture and phenotypic/genotypic DST as gold standard and to assess patient important outcomes.

Trial design	
Prospective, multicentre assessment of Truenat MTB assays and MTB-RIF Dx assay diagnostic accuracy in the intended settings of use.
 
The sample size has been calculated at 1,666 enrolled participants. Sites in India will enrol n= 1,110 participants. Other three global sites will enrol n = 556 participants overall.

Trial sites/setting	India and three other global sites. In India the trial will be conducted at 9 designated microscopy centres (DMC) and 1 private laboratory.
Trial population	Adults with pulmonary tuberculosis symptoms.

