1.3 Benefit/Risk Assessment

Knowledge gained from this trial may benefit society by improving TB diagnosis. Trial participants may directly benefit from the trial because they will be provided with a higher standard of TB diagnostic care than may be routinely available to them.

Given the minimal risks associated with this trial and the potential benefits to society and individuals, the benefits outweigh the aggregated risks. As for any clinical trial, there is a possibility of unknown and unforeseen risk; that possibility is small for this trial. If unforeseen risks are recognized during the trial, then FIND, trial partners, IRBs/ethics committees, and participants must be provided with relevant information.

2 Trial Objectives and Endpoints

Table 1. Trial objectives and endpoints

Objectives	Endpoints
1. Primary	
1.1. Estimate diagnostic accuracy of the Truenat assays (MTB and MTB Plus) for Mycobacterium tuberculosis (MTB) detection among individuals undergoing evaluation for pulmonary TB, overall and per sample, separately for smear-positive and smear-negative TB samples using a culture reference standard.	1.1.1. Sensitivity of the Truenat MTB and MTB Plus assays (including analysis by smear-status and by sample). 1.1.2. Specificity of the Truenat MTB and MTB Plus assays (including analysis by sample).
1.2. Estimate diagnostic accuracy of the Truenat MTB-RIF Dx assay for RIF resistance detection among individuals undergoing evaluation for pulmonary TB and DR TB, using phenotypic/genotypic drug susceptibility testing (DST) ¹ .	1.2.1 Sensitivity of the Truenat MTB-RIF Dx assay 1.2.2 Specificity of the Truenat MTB-RIF Dx assay
2. Secondary	
2.1. Compare the diagnostic accuracy of the Truenat assays (MTB and MTB Plus) and MTB-RIF Dx assay to that of Xpert MTB/RIF, using a reference standard of culture for TB diagnosis	2.1.1. Sensitivity of the Truenat MTB and MTB Plus assays and MTB-RIF Dx assay compared to Xpert MTB/RIF

¹ All samples that exhibit RIF resistance, as determined by either phenotypic DST or Truenat RIF, will be sent for DNA sequencing to determine the mutations responsible for drug resistance. A subset of drug sensitive samples, of approximately matching sample size, will be randomly selected for sequencing, to act as a comparator sequence

and phenotypic/genotypic DST for detection of RIF resistance.	2.1.2. Specificity of the Truenat MTB and MTB Plus assays and MTB-RIF Dx assay compared to Xpert MTB/RIF

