5.3. Minimization of Error and Bias

5.3.1. Patient selection

Spectrum bias will be avoided by enrolling a consecutive series of subjects and using a cross-sectional trial design. Enrolment will be based on clearly defined eligibility criteria, targeting patients suspected to have TB as defined by WHO12, thus representing future target populations. Descriptive statistics on patient characteristics and estimates of diagnostic accuracy stratified by site, smear and HIV status to further ensure the validity and generalizability of trial results will be provided.

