10.2. Sample Size Determination

The sample size was chosen to achieve high confidence in the accuracy estimates for MTB-detection and RIF resistance detection for the overall multi-country trial for which the Indian trial is one of the countries.

Based on an expected sensitivity of Truenat MTB plus for detection of TB among smear-negative/culture-positive cases of 67% (based on preliminary data), 80 smear-negative/culture-positive cases would be required to achieve a total width of the 95% confidence interval of 20% (95%CI: 57 to 77). Assuming a TB prevalence of 20% and a prevalence of smear-negative/culture-positive cases among TB cases of 30%, the total number of subjects to be enrolled would be 1,333. To account for losses, this is inflated by 20%, yielding a final sample size of 1,666 participants under investigation for TB overall.

In India, two thirds of these trial participants will be recruited i.e. $n = 1,110$ thus 67 smear-negative/culture-positive cases and a 95% confidence interval of 21% could be achieved (95%CI 55 to 79).

The other one-third of enrolled participants ($n = 556$) will be recruited in three other countries in order to provide geographic variation.

The secondary objective of determining diagnostic accuracy of RIF resistance by Truenat MTB is based upon an expected Truenat RIF sensitivity of 95% with a confidence interval of 10% (90-100%), requiring $n=37$ RIF-resistant participants detected. Assuming a prevalence of 20% culture-positive TB cases detected across all presumed TB cases, and 2.8% RIF resistance amongst all culture-positive TB cases and 12% prevalence of RIF resistance amongst TB retreatment cases, we predict 1,542 re-treatment patients would thus need to be enrolled. While the prevalence of culture-positive TB cases may be higher if enrolment is conducted at a drug-resistance TB referral clinic, we conservatively accept that this may not be the case. As such, we may not reach sufficient sample size to allow analysis of secondary objectives in this trial. Detection of RIF resistance will be continually monitored throughout the trial, and any possible shortfall will be supplemented with a future sub-study, if needed, using confirmed RIF-resistant sputum samples from the FIND specimen bank of cryopreserved samples. We will place an enrolment cap of 200 enrolled participants in the drug resistance group for the entire trial, in order to not undermine the primary objective of enrolment of smear-negative culture

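### On its own inputs the protocol expects about 10 to 14 of the 37 RIF-resistant participants it requires, and its rule for the shortfall does not say that frozen bank samples stay out of the primary RIF sensitivity

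*Protocol*

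**What the plan says.** The synopsis, section 2 (Table 1) and section 10.1 all list sensitivity of the Truenat MTB-RIF Dx assay as a primary outcome. The Table 1 objective is: "Estimate diagnostic accuracy of the Truenat MTB-RIF Dx assay for RIF resistance detection among individuals undergoing evaluation for pulmonary TB and DR TB". The synopsis sets the primary objectives as "using culture and phenotypic/genotypic drug susceptibility test (DST) as gold standard in the intended setting of use".

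Section 10.2, which labels the RIF objective secondary, plans on a sensitivity of 95% with an interval of 90-100%, "requiring $n=37$ RIF-resistant participants detected". Its inputs are "Assuming a prevalence of 20% culture-positive TB cases detected across all presumed TB cases", then "2.8% RIF resistance amongst all culture-positive TB cases", and 12% resistance among retreatment cases. From these it derives a need for 1,542 retreatment patients. It then caps the Drug Resistant group at 200 for the whole trial, concedes that the sample may be too small, and says that resistance will be monitored. The remedy is that "any possible shortfall will be supplemented with a future sub-study, if needed, using confirmed RIF-resistant sputum samples from the FIND specimen bank"; these samples are cryopreserved. No expected number of resistant participants is given.

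**The concern.** There are two linked problems.

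First, the section puts a required number and a precision beside a cap that, on the section's own rates, cannot deliver them. A reader who sees 37 cases and 90-100% will expect an informative RIF sensitivity from this trial. Nothing tells that reader that about a third of the number is expected.

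Second, the rule for the gap speaks of supplementing the shortfall, and the shortfall is in the count of resistant participants. That wording can be read as permission to add bank samples until 37 is reached. Those samples are selected because they are already known to be resistant, come from people not enrolled consecutively in this trial, and are frozen. Only resistant samples would be added, so sensitivity and specificity would describe different sources. The resulting figure would sit badly under an objective about people being evaluated in the intended setting of use. It would also sit badly beside section 5.3.1, which says "Spectrum bias will be avoided by enrolling a consecutive series of subjects and using a cross-sectional trial design".

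**Working it through.** **Inputs, all from section 10.2 unless noted.** Total enrolment 1,666, including 20% for losses; Drug Resistant group cap 200; culture-positive 20%; RIF resistance 2.8% among all culture-positive cases and 12% among retreatment cases; required resistant cases 37; planned sensitivity 95%. The interval method is Wilson (section 10.5.2).

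**The plan's own figures.**
- Retreatment patients needed: 37 / (0.20 × 0.12) = 1,541.7, so 1,542 reproduces.
- Total enrolment: 80 / (0.20 × 0.30) = 1,333, and 1,333 / 0.80 = 1,666. This also reproduces.
- The 37 does not reproduce the stated interval. A Wald interval of 95% ± 5 points needs 1.96² × 0.95 × 0.05 / 0.05² = 73 cases. That is a separate point. It is noted here because even a full 37 would not give 90-100%.

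**Expected resistant participants.** The formula is (Case Detection number × 0.20 × 0.028) + (200 × 0.20 × 0.12).

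| Reading of the cap | Before losses | After 20% losses |
|---|---|---|
| 200 inside the 1,666 | 8.2 + 4.8 = 13.0 | 10.4 |
| 200 added to 1,666 | 9.3 + 4.8 = 14.1 | 11.3 |

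So about 10 to 14 are expected, or 28-38% of 37 (10.4/37 to 14.1/37). With a mean of 13, the Poisson 95% range is 6 to 21, so chance alone would not bring the count to 37. Only different input rates would.

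**Precision.** The Wilson limits are [p + z²/2n ± z√(p(1−p)/n + z²/4n²)] / (1 + z²/n), with p = 0.95 and z = 1.96.

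| n | 95% interval | Width (points) |
|---|---|---|
| 10 | 65.5-99.5% | 33.9 |
| 13 | 70.1-99.4% | 29.2 |
| 14 | 71.3-99.3% | 28.0 |
| 20 | 76.4-99.1% | 22.7 |
| 27 | 79.9-98.9% | 19.0 |
| 37 | 82.9-98.7% | 15.8 |

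**Sensitivity to the Drug Resistant group's yield** (assumed values, cap inside 1,666). Cases = 8.2 + 200 × culture positivity × resistance.

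| Culture-positive | Resistance | Before losses | After losses |
|---|---|---|---|
| 50% | 12% | 20.2 | 16.2 |
| 80% | 12% | 27.4 | 21.9 |
| 100% | 12% | 32.2 | 25.8 |
| 50% | 30% | 38.2 | 30.6 |

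With 12% resistance held, no culture positivity reaches 37. Raising resistance as well can close the gap.

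**Share from the bank if pooled to exactly 37.** 1 − 14.1/37 = 62% to 1 − 10.4/37 = 72%. At 20 or 27 prospective cases before losses the share falls to 45% or 26%.

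**The case against.** The strongest reply is that the protocol contains no pooling rule, and several sections point the other way.
- Section 10.2 speaks of a future sub-study, to be done only if needed.
- Section 5.2 allows device testing only on samples from enrolled participants.
- Table 4 (section 10.3) defines the Enrolled and Evaluable sets as participants and has no bank-specimen population.
- Section 10.5.2 bases the RIF analysis on patients.
- The change log for Draft 3.1 gives a separate laboratory study as the reason for removing frozen samples. This is history only, but it is consistent with separation.

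This stands. A reader might infer that most of the primary RIF sample will be bank sputum, that the estimate will be biased upward, or that its interval will look about twice as tight as the prospective evidence supports. The documents support none of these as fact. The share and the narrower interval follow only under pooling, and the documents give no difference between bank and prospective sensitivity, in either size or direction. Nor does section 5.3.1 conflict with a sub-study kept separate, because it governs enrolment into this trial.

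The second reply is that the inputs are cautious. Section 10.2 says culture positivity may be higher at a referral clinic and calls its assumption conservative. It also says drug-resistant cases are more likely to be culture-positive. The group consists of treatment failures (section 4.1), and one site is an MDR reference hospital (section 4). This also stands, so near-certainty of a shortfall cannot be claimed. What can be said is that a shortfall is expected on the inputs the plan adopted.

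Third, the section does concede that numbers may be insufficient. That is fair, but the concession carries no count and no interval.

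Finally, rules for combining data may be left to an SAP, which is not at hand. But section 10.2 itself sets the supplementation rule, so its wording should be corrected there.

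**Conclusion.** The point holds in a limited form. On section 10.2's own rates, a primary endpoint said to need 37 resistant participants is expected to get about 10 to 14, with a Wilson interval about 28 to 34 points wide at 95% sensitivity. This rests on 20% culture positivity and 12% resistance in the Drug Resistant group. If culture positivity there were 50-80%, the count would be about 20 to 27 before losses and still below 37. The counts are of resistant participants. Only samples positive on Truenat MTB go on to the RIF chip (section 8.1), so the usable denominator would be no larger.

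The wording on supplementation leaves room for bank samples to enter the primary estimate, although the analysis sections suggest they would not. The 62-72% bank share is the consequence if they did, not a description of what the protocol plans. The point merits correction before analysis, but it does not invalidate the design.

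**What to change.** In section 10.2:
1. State the expected number of prospective RIF-resistant participants (about 10 to 14 on the stated inputs), with the range under a higher yield in the Drug Resistant group, and describe the shortfall as expected on those inputs.
2. Give the matching Wilson widths (about 28 to 34 points for 10 to 14 cases, and about 23 and 19 points for 20 and 27) beside or in place of 90-100%.
3. State that primary RIF sensitivity and its interval use only prospectively enrolled participants with a Truenat RIF result, whatever their number.
4. Replace the supplementation wording with a statement that any bank-sample sub-study is reported separately and never added to the prospective numerator or denominator.

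Repeat items 3 and 4 in the SAP. The cost is wording and a wider stated interval for a primary endpoint; no extra participants or tests are needed. If separate reporting was always intended, items 3 and 4 only make that explicit.

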10.3. Populations for Analyses

For purposes of analysis, the following participant populations are defined:

Table 4. Populations for analyses

Population	Description
Enrolled	All participants who sign the ICF
Evaluable	All participants with a culture positive or culture negative results. Contaminated cultures will be excluded. Contamination is defined as below:
Smear-positive	≥ 1 positive smear (inclusive of scanty positive smears). Smear positives with only negative or contaminated cultures will be excluded from analysis.
Culture-positive	≥ 1 LJ and/or MGIT culture growth confirmed MTB complex. Cross-Contamination: A single LJ culture with ≤ 20 colonies or a single MGIT culture with MTB growth ≥28 days per patient will be excluded from analysis.
Culture-negative	At least 2 LJ or MGIT have no culture growth after >56 days and >42 days
Contaminated culture	LJ: Cultures completely overgrown by bacterial or fungal contaminations within 3 weeks (discarded). In case of mixed cultures, isolated MTB colonies transferred to new LJ tube (repeat culture). MGIT: Instrument positivity tests for confirmation of MTB complex negative. 2 contaminated cultures will lead to exclusion of this patient from analysis unless other criteria for culture-positivity/negativity are met
Xpert-positive	MTB positive on Xpert® MTB/RIF.
Xpert-negative	MTB negative on Xpert® MTB/RIF.
Xpert-indeterminate	Any indeterminate, error, or inability to produce a result from a single Xpert® MTB/RIF run.
Non-TB case	Smear-negative, Xpert-negative and culture-negative and not started on TB treatment on the basis of clinical criteria. NTM: Specimens with growth of mycobacteria other than MTB complex only.
Clinical TB case	Any participant who tests smear-negative, Xpert-negative, culture-negative but is started on TB treatment on the basis of clinical criteria.

Phenotypic RIF resistant	Culture-positive and growth for RIF on MGIT SIRE DST testing.
Phenotypic RIF sensitive	Culture-positive and no growth for RIF on MGIT SIRE DST testing
Genotypic RIF resistant	Sequencing identifies mutations recognized to be associated with RIF-resistance (defined based on consultation with WHO prior to analysis)
Genotypic RIF sensitive	Sequencing identifies no mutations recognized to be associated with RIF-resistance (defined based on consultation with WHO prior to analysis)
Composite reference standard RIF resistant	
If phenotypic DST shows sensitivity but sequencing identifies mutations recognized to be associated with resistance, the composite reference standard will be considered RIF-resistant.
 
If phenotypic DST shows resistance but sequencing does not identify mutations to be associated with resistance, the composite reference standard will be considered RIF-resistant (as mutations will be assumed outside of the region sequenced).

Safety	All participants assigned to trial intervention.

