10.5.2. Analysis of Primary Outcomes

Analyses of the diagnostic accuracy of the index test will be done according to the case definitions. Table 6 summarizes the way diagnostic tests results are usually reported when comparing the index test results to a reference standard. Based on the definitions in the table, the following values are defined:

Sensitivity = $TP / (TP + FN)$

Specificity = $TN / (FP + TN)$

Table 6. Definition of classification metrics

Test result	Case definition			
		TB	Non-TB	Total
	Detected	TP	FP	TP + FP
	Not detected	FN	TN	FN + TN
	Total	TP + FP	FP + TN	All

Abbreviations: TB=true positive, FP=false positive, FN=false negative, TN=true negative

Only patients with uncontaminated culture results and without indeterminate test results will be included in the analysis of performance characteristics for MTB detection. Similarly, such patients will contribute to the analysis of the performance characteristics for RIF detection. For each point estimate, a 95% confidence interval will be derived based on Wilson score. Missing data and invalid results will be reported in the descriptive tables, and will not be imputed.

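### Table 4 contradicts itself on cultures that grow only non-tuberculous mycobacteria (NTM), so some of these participants drop out of the specificity denominator

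*Protocol*

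**What the plan says.** All the definitions stand in Protocol Section 10.3, Table 4.

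- **Contaminated culture, MGIT:** "MGIT: Instrument positivity tests for confirmation of MTB complex negative". No step separates mycobacterial growth from bacterial or fungal growth.
- **Contaminated culture, LJ:** limited to bacterial or fungal overgrowth within three weeks.
- **Consequence:** "2 contaminated cultures will lead to exclusion of this patient from analysis unless other criteria for culture-positivity/negativity are met".
- **Culture-negative:** "At least 2 LJ or MGIT have no culture growth after >56 days and >42 days".
- **Non-TB case:** the row opens with "Smear-negative, Xpert-negative and culture-negative and not started on TB treatment on the basis of clinical criteria" and then adds "NTM: Specimens with growth of mycobacteria other than MTB complex only".
- **Smear-positive:** participants with a positive smear whose cultures are all negative or contaminated are excluded from analysis.
- **Evaluable:** "All participants with a culture positive or culture negative results. Contaminated cultures will be excluded".

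Section 10.5.2 carries this into the primary analysis: "Only patients with uncontaminated culture results and without indeterminate test results will be included in the analysis of performance characteristics for MTB detection". Specificity of the two MTB assays is primary endpoint 1.1.2 in Table 1. Section 5.3.3 sets the reference standard at two MGIT and two LJ cultures.

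**The concern.** The same culture result is given two opposite meanings. An MGIT tube that grows NTM is instrument-positive and MTB-complex-negative. The contamination row makes it non-evaluable, and the Non-TB row makes it evidence of a non-case. On LJ the same organism is not contamination, not absence of growth and not MTB, so it falls outside every culture class. The Non-TB row is also at odds with itself: its first sentence requires culture-negative status, which Table 4 defines as no growth, and its second admits NTM growth.

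At stake is who counts in the denominator of a primary endpoint. Two analysts following the protocol faithfully could place the same participant differently. The participants affected are those with repeated NTM growth, who would carry most of the trial's information on how the assays behave when other mycobacteria are present.

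**Working it through.** **1. Applying Table 4 to every NTM-only result.** Take two MGIT and two LJ cultures, each showing either no growth or NTM growth, with at least one NTM and no MTB. That gives 2^4 − 1 = 15 patterns. The culture-negative rule can be read as any two no-growth cultures, or as two no-growth cultures on the same medium. Smear-negative participants are assumed.

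| NTM growth in | Patterns | Any two no-growth | Two on same medium |
|---|---|---|---|
| one culture | 4 | culture-negative | culture-negative |
| both MGIT only, or both LJ only | 2 | culture-negative | culture-negative |
| one MGIT and one LJ | 4 | culture-negative | unclassified |
| one MGIT and both LJ | 2 | unclassified | unclassified |
| both MGIT and one LJ | 2 | excluded | excluded |
| all four | 1 | excluded | excluded |

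Totals under the first reading are 10 retained, 3 excluded and 2 unclassified. Under the second they are 6, 3 and 6. Unclassified participants are neither culture-positive nor culture-negative, so they are not Evaluable. These are counts of patterns, not probabilities.

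**2. Smear-positive participants.** A participant with NTM in both MGITs and two no-growth LJs meets the culture-negative rule. If smear-positive, that participant has only contaminated or negative cultures and is removed by the smear row.

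**3. Anchor for an illustration.** Section 10.2 assumes 20% TB prevalence, a 30% smear-negative share and 80 target cases: 80 / (0.20 × 0.30) = 1,333, and 1,333 / 0.80 = 1,666, as stated. The non-TB group before losses is then 1,333 × 0.80 = 1,066.

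**4. Effect on specificity.** The protocol gives no NTM share (f), cross-reaction rate (x) or expected specificity. Assume 98% specificity in other non-TB participants and, as the extreme case, that every NTM participant is lost.

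- NTM excluded: 98.0%
- NTM counted as non-TB: 0.98(1 − f) + (1 − x)f = 0.98 − f(x − 0.02)
- Difference (excluded minus counted): f(x − 0.02)

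Specificity with NTM counted:

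| f (participants) | x = 0 | x = 10% | x = 50% |
|---|---|---|---|
| 1% (11) | 98.0% | 97.9% | 97.5% |
| 5% (53) | 98.1% | 97.6% | 95.6% |
| 10% (107) | 98.2% | 97.2% | 93.2% |

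At f = 5% and x = 10% the difference is 0.05 × 0.08 = 0.4 point. At f = 5% and x = 0 it is 0.05 × (−0.02) = −0.1 point, so exclusion would understate specificity. For scale, the 95% half-width at 98% and n = 1,066 is 1.96 × √(0.98 × 0.02 / 1,066), about 0.8 point.

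**The case against.** The strongest case on the other side is that this is a small wording conflict, and that several inferences a reader might draw from it do not hold.

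- **That all NTM participants are excluded.** Not so. Exclusion needs two contaminated cultures and is lifted when the culture-negative criteria are met. Most patterns survive under the lenient reading.
- **That specificity can only be overstated.** The formula shows that the direction depends on whether NTM participants test positive more often than other non-TB participants. The protocol does not say. The false-positive mechanism it names is residual DNA after recent TB (Section 7.1), for which Section 10.5.5 plans specificity by TB history.
- **That cross-reactions are hidden.** Section 5.3.5 says samples with contaminated cultures are excluded from the main accuracy analyses but reported separately. They leave the denominator, not the report.
- **That sites will classify differently.** Table 4 defines analysis populations and Section 12.3 gives data management to the sponsor. Nothing says that sites assign these classes.

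All four limits stand. Section 10.4 also leaves description of the analysis populations to the SAP, which is not at hand and could settle which row takes precedence.

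None of this removes the contradiction. Table 4 already states the definitions, and a participant with NTM in all four cultures is excluded by one row and non-TB by another. The separate reporting in Section 5.3.5 covers contaminated cultures together. It does not call for NTM to be split out, and it does not reach NTM growth on LJ, which is not classed as contaminated.

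**Conclusion.** The point holds as an internal contradiction that affects a primary endpoint for a limited group: participants with NTM growth in enough cultures that the no-growth requirement fails, and some smear-positive participants with less NTM growth. It does not support a claim that specificity is biased in a known direction or by a known amount. The 0.4-point figure rests on assumed values of 5% NTM, 10% cross-reaction and 98% specificity elsewhere. It is an upper bound for those values, because Table 4 does not remove every NTM participant. Higher assumed rates give larger differences, and zero cross-reaction reverses the sign. The table should be corrected because the rule is stated, bears on the primary analysis and is cheap to repair.

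**What to change.** In Table 4:

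1. Limit contaminated MGIT to growth that is not mycobacterial, in line with the LJ wording.
2. Add an NTM-only class for both MGIT and LJ: mycobacterial growth, MTB complex negative, and no MTB in any culture. State that it counts as non-TB in the specificity denominator.
3. Reconcile the smear-positive exclusion with this class.
4. Report specificity with and without the NTM-only group.

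The cost is table wording and one extra tabulation, plus one laboratory detail. Sections 5.3.3 and 8.1 already provide MPT64 and/or line probe identification of positive cultures, but a result negative for MTB complex does not by itself separate NTM from other growth. The protocol describes no check that does, such as acid-fast staining of the positive culture, and it should name one. The Non-TB row already presupposes that this distinction can be made.
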